4.2 INCLUSION CRITERIA

Each subject must meet the following criteria to be enrolled into the study:

- Evidence of a personally signed and dated informed consent document
- Is willing and able to comply with scheduled visits, treatment plan, laboratory tests, and other study procedures and is deemed an appropriate candidate for participation in this long-term extension study
- Eligible female subjects will be:
 - Nonpregnant, evidenced by a negative serum hCG pregnancy test at Baseline
 - Nonlactating
 - Surgically sterile or postmenopausal, or agree to continue to use an accepted method of birth control for at least 3 months prior to first dose, during, and for at least 30 days after last study drug administration
 - Acceptable methods of birth control are: hormonal contraceptives, double barrier method, intrauterine device, surgical sterility for at least **6 months** prior to Screening for tubal ligation performed laparoscopically, surgical sterility for at least **6 months** prior to Screening by hysterectomy and/or bilateral oophorectomy, and/or postmenopausal status (defined as at least **2 years** without menses). Intended abstinence is not considered an acceptable method

of birth control for this study; subjects must agree to use an acceptable method of birth control should they become sexually active during the study or within **30 days** after the last dose of study drug.

- Eligible male subjects will either be:
 - Surgically sterile (ie, vasectomy) for at least 3 months prior to Screening
 - Agree to use a condom with spermicide when sexually active with a female partner who is not using an acceptable method of birth control during the study and for 30 days after last study drug administration
- Eligible male and female subjects must agree not to participate in a conception process (ie, active attempt to become pregnant or impregnation, sperm donation, in vitro fertilization) during the study and for 30 days after the last dose of study drug
- Fulfilled all eligibility criteria for Study APD811-003 and completed the study as planned
 - Subjects who were assigned to placebo in Study APD811-003 and experienced clinical worsening in that study may enroll in Study APD811-007 after he/she has completed all end of study procedures per protocol, including RHC, and have had their individual Study APD811-003 data locked.

4.3 EXCLUSION CRITERIA

Subjects who meet any of the following criteria will be excluded from the study:

- Subjects who enrolled in Study APD811-003 and were withdrawn from study drug treatment due to any AE or SAE, or subjects who did not complete Study APD811-003, with the exception made as above for placebo-treated subjects who experienced a clinical worsening event.
- Female subjects who wish to become pregnant
- Systolic BP <90 mmHg at Baseline
- Other severe acute or chronic medical or laboratory abnormality that may increase the risk associated with study participation or investigational product administration or may interfere with the interpretation of study results and, in the judgment of the Investigator, would make the subject inappropriate for entry into this study.

5 STUDY TREATMENTS

5.1 TEST ARTICLE

The Sponsor will provide adequate supplies of ralinepag IR capsules. Ralinepag will be provided as 10, 20, 30, 40, and 100 mcg IR dose strengths, and later will be provided as 50, 250, and 400 mcg (0.05, 0.25, and 0.4 mg) XR tablet dose strengths.

5.2 TREATMENTS ADMINISTERED

The ralinepag IR formulation initially used in the study is a liquid-filled, size 4, hard-gelatin capsule containing ralinepag, polyoxyl 40 hydrogenated castor oil (Kolliphor[®] RH40) NF, butylated hydroxytoluene NF, and colloidal silicon dioxide NF. The ralinepag XR formulation tablet contains ralinepag, hydroxypropylmethyl cellulose (Methocel K4M Premium CF and Methocel K100 Premium LVCR), microcrystalline cellulose (Avicel PH102), mannitol (Pearlitol 100 SD), silicon dioxide, and magnesium stearate.

Ralinepag used for the capsules was manufactured under Current Good Manufacturing Practices compliance by the Sponsor (or designee). The APD811 capsules (IR) or tablets (XR) will be manufactured under Current Good Manufacturing Practices compliance by the Sponsor (or designee).

5.3 PACKAGING, LABELING AND STORAGE

For each IR formulation dosage strength, 74 capsules will be bulk packaged in 40-cc high-density polyethylene bottles with a heat induction seal and child-resistant screw caps. These bottles should be stored under refrigeration at 2°C (36°F) to 8°C (46°F); the bottles should not be frozen.

XR tablets are packaged in PERLALUX[®] blisters (polyvinyl chloride [PVC]/polyethylene/polyvinylidene chloride [PVDC], 250/30/90, and cover foil Alu 20 mcm) in a 1×8 configuration and carded in an 8×8 array, 64 tablets per card. The cards are stored at 15°C to 30°C (59°F to 86°F).

5.4 TEST ARTICLE ACCOUNTABILITY

The Investigator will maintain accurate records of the receipt of all study drug. In addition, accurate records will be kept regarding when and how much study drug is dispensed and used by each subject in the study. Reasons for deviation from the expected dispensing regimen must also be recorded. Study drug will be reconciled by the Sponsor's monitor or contracted designee. The Investigator agrees to provide sufficient access to study drug as required for the reconciliation process to be completed in a timely fashion.

5.5 INVESTIGATIONAL PRODUCT RETENTION AT STUDY SITE

At completion of the study, all study drug will be reconciled by the Sponsor's monitor or contracted designee and then returned to either the Sponsor or a third-party contractor to be retained or destroyed according to applicable country regulations and investigative site SOPs. Prior to any action being taken with study drug after the study is completed, the Investigator will contact the Sponsor (or contracted CRO) for approval of such action.

5.6 DOSAGE AND ADMINISTRATION

Investigational product will be dispensed to the subjects under the supervision of the Investigator or his/her designee. Subjects should not crush, break, chew, or dissolve the capsules or tablets. Subjects should wash hands with soap and water after handling drug product.

Capsules or tablets should be taken with food.

5.6.1 *Immediate-release Capsules*

5.6.1.1 *Dose Titration Period (Study APD811-003 Placebo-treated Subjects)*

Subjects who were assigned to placebo treatment in Study APD811-003 will undergo a Dose Titration Period of up to 9 weeks. All subjects will be on active treatment (ralinepag) in the open-label study, APD811-007.

The dose titration scheme will be the same as conducted in Study APD811-003. Subsequent dose escalations will continue until the MTD is determined, with a possible maximum total daily dose of 600 mcg (300 mcg BID) if tolerated. Subjects will be observed for at least 4 hours after the initial dose of ralinepag, and at each subsequent dose escalation. AEs, BP, and heart rate will be monitored during the observation period. The observation period may be extended based on the judgment of the Investigator. If deemed necessary by the Investigator, the subject may be monitored as an inpatient for the initial dose and/or subsequent increases in dose. The medical monitor should be notified in any instance that prolonged observation and/or inpatient monitoring is anticipated or required.

If a dose is not tolerated, the study drug should be decreased to the previous dose level. If the initial dose of 10 mcg BID is not tolerated, dosing may be decreased to 10 mcg QD.

If the initial dose is tolerated (10 mcg BID), then the dose will be increased in the following fashion at subsequent visits: 20, 30, 40, 60, 80, 100, 200, and 300 mcg BID. The dose may be escalated to a possible maximum total daily dose of 600 mcg (300 mcg BID) if tolerated.

Subjects may become symptomatic during the course of dose escalation, and adjustment up and/or down may be required to find the optimal dose for any given subject. Over the 9-week Dose Titration Period, there are opportunities to change the dose. If a particular dose is not tolerated, treatment may be reduced to a previous dose as directed by the Investigator. The dose may be decreased for safety/tolerability reasons at any time, but may not be increased without assessment in the clinic.

Table 3 indicates the dosing regimen during the Dose Titration Period.

Prolonged dosing may result in tolerance to some adverse effects, so that consideration should be made to attempt dose escalation if some time (eg, >7 days) has elapsed since the prior dose escalation attempt and the 9-week Dose Titration Period is not yet complete.

In order to simplify dose titration, the 10 mcg strength capsule will be used during the initial portion of the dose titration.

If a subject reaches the highest dose tolerated (stable dose) and no further dose escalations are planned, the Dose Titration Period will be considered completed.

Table 3 Possible Dosing Regimen during 9-Week Dose Titration Period

Dose (mcg)		Supplied by		Total daily dose (mcg)
10	QD	1 × 10 mcg	QD	10
10	BID	1 × 10 mcg	BID	20
20	BID	2 × 10 mcg	BID	40
30	BID	3 × 10 mcg	BID	60
40	BID	4 × 10 mcg	BID	80
60	BID	3 × 20 mcg	BID	120
80	BID	4 × 20 mcg	BID	160
100	BID	5 × 20 mcg	BID	200
200	BID	2 × 100 mcg	BID	400
300	BID	3 × 100 mcg	BID	600

Abbreviations: BID, twice daily; QD, once daily

5.6.1.2 Treatment Period

Subjects who were on active treatment (ralinepag) in Study APD811-003 will remain on current dose and have onsite clinical assessments performed every 3 months until the subject is discontinued from the study (see Table 1). Subjects in the placebo treatment group of Study APD811-003 will undergo a Dose Titration Period until a stable MTD is reached (up to 9 weeks). At the conclusion of the Dose Titration Period and when a subject reaches the highest dose tolerated, the subject will transition directly into the Treatment Period with monthly assessments for the first 3 months and then every 3 months.

The optimal dose achieved for each subject at the end of the Dose Titration Period can be maintained throughout the Treatment Period; however, incremental dose increases will also be allowed during the Treatment Period at the discretion of the Investigator (as clinically indicated) and according to the stepwise titration scheme outlined in Table 4.

Table 4 indicates the possible IR dosing regimens to be used during the remainder of the Treatment Period according to each individual subject's optimally defined dose.

Table 4 Possible Dosing Regimen during the Treatment Period

Dose (mcg)		Supplied by		Total daily dose (mcg)
10	QD	1 × 0.01 mcg	QD	10
10	BID	1 × 0.01 mcg	BID	20
20	BID	1 × 0.02 mcg	BID	40
30	BID	1 × 0.03 mcg	BID	60
40	BID	1 × 0.04 mcg	BID	80
60	BID	2 × 0.03 mcg	BID	120
80	BID	2 × 0.04 mcg	BID	160
100	BID	1 × 0.1 mcg	BID	200
200	BID	2 × 0.1 mcg	BID	400
300	BID	3 × 0.1 mcg	BID	600

Abbreviations: BID, twice daily; QD, once daily

5.6.2 *Extended-release Tablets***5.6.2.1** *Formulation Switch and Dose Titration Period*

During the study, all subjects will switch to an XR formulation of ralinepag that will be used in Phase 3 studies of ralinepag, per the guidance in Table 5. The switch to XR ralinepag should occur at a regularly scheduled visit, with dose titration to occur, as needed, in 50-mcg weekly increments. Weekly phone contact with the subject will be performed to guide XR dose titration to the highest tolerated dose.

Table 5 Dose Switching Guidance from Immediate-release to Extended-release Ralinepag

Current IR Dose (mcg; total daily)	Corresponding XR Dose (mcg)
<30	50 EOD
≥30 to <120	50
120	100
160	150
200	200
400	400
600	600

Abbreviations: EOD, every other day; IR, immediate-release; XR, extended-release

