Study APD811-003 was a randomized, double-blind, parallel-group, placebo-controlled, Phase 2 study of ralinepag in subjects with PAH. In this 61-subject study, the primary efficacy analysis demonstrated a statistically significant absolute change from Baseline in PVR compared to placebo. Ralinepag also demonstrated numerical improvement in 6-Minute Walk Distance (6MWD). Ralinepag improved median PVR by 163.9 dyn.s.cm⁻⁵ from baseline compared to a 0.7 dyn.s.cm⁻⁵ worsening from baseline in the placebo arm (p=0.02). Subjects treated with ralinepag had a 29.8% reduction in PVR compared to the placebo arm (p=0.03) and a 20.1% reduction in PVR compared to baseline. Additionally, AEs observed in the study were consistent with other prostacyclin treatments for the management of PAH, with headache, nausea, diarrhea, jaw pain, and flushing being the most commonly reported AEs. Additional information is be presented in the Investigator's Brochure.

In Study APD811-011, an extended-release (XR) tablet formulation of ralinepag was evaluated in a dose escalation paradigm over approximately 4 weeks (with daily dosing starting at 60 mcg and slowly up-titrating, depending upon individual subject tolerability, by

additional 60 mcg dose increments every 5 days up to 30 mcg) in healthy subjects in both the fasted and fed states.

The data from this study showed that ralinepag peak and total plasma exposure for the XR tablet were dose dependent (appearing only slightly higher than dose proportional) and did not appreciably vary when taken with or without food. Lastly, the XR tablet shows a higher plasma concentration at 24 h compared to the immediate-release (IR) capsule, indicating an improved plasma PK performance over the IR capsule with respect to once-daily dosing in terms of extending exposure and minimizing peak-to-trough fluctuation.

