5.6.2.2 Treatment Period

After the dose switch and Dose Titration Period with the XR formulation, subjects will continue into the Treatment Period, in which subjects will have an assessment every 3 months. With the exception of the difference in ralinepag formulation, this Treatment Period will be identical to that which occurred with the IR formulation (Section 5.6.1.1, Section 7.2.3).

The optimal dose achieved for each period during the Formulation Switch and Dose Titration Period (Section 5.6.1.1) can be maintained; however, incremental dose changes (uptitration or down titration) will also be allowed during the Treatment Period at the discretion of the Investigator (as clinically indicated).

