7.2.3.3 Switch to XR Ralinepag and Dose Titration

At 1 of the regular quarterly visits, as outlined in Section 7.2.3.1, in addition to the regularly scheduled procedures, subjects will be given new dosing cards with an XR formulation of ralinepag. Dose-switching will occur as outlined in Table 5, and titration will occur as

described in Section 5.6.2.1 via weekly telephone calls until the next regularly scheduled quarterly visit, at which time the subject will resume procedures described in Section 7.2.3.1.

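### The protocol contradicts itself on whether the 600 mcg/day maximum and the clinic-assessment condition, both stated for IR titration, also apply to XR titration

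*Protocol*

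**What the plan says.** **IR titration (Protocol 5.6.1.1).** This section covers subjects who received placebo in APD811-003. Doses rise until the maximum tolerated dose is found, "with a possible maximum total daily dose of 600 mcg (300 mcg BID) if tolerated", and the section gives this maximum twice. The dose may be lowered at any time "but may not be increased without assessment in the clinic". Each escalation is followed by at least 4 hours of observation.

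**XR titration (Protocol 5.6.2.1 and 7.2.3.3).** All subjects switch to XR at a scheduled visit, using Table 5 ("Dose Switching Guidance from Immediate-release to Extended-release Ralinepag"), "with dose titration to occur, as needed, in 50-mcg weekly increments". The end point is set by this sentence: "Weekly phone contact with the subject will be performed to guide XR dose titration to the highest tolerated dose". Section 7.2.3.3 says titration runs "via weekly telephone calls until the next regularly scheduled quarterly visit". Neither section states a maximum or asks for a clinic assessment before an increase.

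**Increases during the Treatment Period (Protocol 3.1 and 5.6.1.2).** A paragraph in Section 3.1 opens by naming both formulations in connection with dose reductions. Its next sentence ties Treatment Period increases to Table 4, whose top row is 600 mcg/day. Section 5.6.1.2 describes Table 4 as a table of IR regimens.

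**XR Treatment Period (Protocol 5.6.2.2).** Apart from formulation, this period is said to be identical to the IR one, for which Sections 5.6.1.1 and 7.2.3 are cited. The next paragraph reads: "The optimal dose achieved for each period during the Formulation Switch and Dose Titration Period (Section 5.6.1.1) can be maintained". It then allows uptitration at the Investigator's discretion and does not mention Table 4.

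**The concern.** A site looking for the upper limit on XR dosing, or asking whether an increase may be agreed by telephone, gets different answers from different sections. Section 5.6.2.1 alone gives no limit and a telephone procedure. Section 3.1 can be read as giving a limit of 600 mcg/day. The citation of Section 5.6.1.1 in Section 5.6.2.2, taken literally, brings in both the 600 mcg/day maximum and the clinic condition, and the clinic condition conflicts with the telephone titration in 5.6.2.1 and 7.2.3.3.

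What is at stake is subject safety. A site could follow Section 5.6.2.1 exactly and go above the only daily maximum the protocol states, without a clinic visit in between. Another site could follow a different section and stop at 600.

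**Working it through.** **1. The plan's own figure.** 300 mcg twice daily = 2 × 300 = 600 mcg/day. This matches the last rows of Tables 3 and 4.

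**2. Does Table 4 fit XR titration?** Its total daily doses are 10, 20, 40, 60, 80, 120, 160, 200, 400 and 600 mcg. The successive steps are 10, 20, 20, 20, 40, 40, 40, 200 and 200 mcg. None is 50 mcg, and the XR doses of 100 and 150 mcg in Table 5 are not rows of Table 4. So Table 4 cannot serve as the XR step scheme, although its top row could still be meant as a ceiling.

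**3. What Section 5.6.2.1 permits when read alone.** Inputs:
- XR starting doses from Table 5: 50, 100, 150, 200, 400 and 600 mcg daily. The 50 mcg every-other-day row is left out because its titration path is not defined.
- Step: 50 mcg per week (5.6.2.1).
- Duration: from the switch visit to the next quarterly visit (7.2.3.3). A quarter is taken as 91 days, which is an assumption.
- Visit window: ±5 days for each quarterly visit (6.15), so two visits lie 91 − 10 = 81 to 91 + 10 = 101 days apart.

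Number of weekly steps strictly before the next visit: k = floor((days − 1)/7).
- 91 days: floor(90/7) = 12
- 81 days: floor(80/7) = 11
- 101 days: floor(100/7) = 14

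Highest dose = start + 50 × k:

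| XR start (mcg) | k = 11 | k = 12 | k = 14 | k = 12, relative to 600 | Steps needed to pass 600 |
|---|---|---|---|---|---|
| 50 | 600 | 650 | 750 | 1.08 | 12 |
| 100 | 650 | 700 | 800 | 1.17 | 11 |
| 150 | 700 | 750 | 850 | 1.25 | 10 |
| 200 | 750 | 800 | 900 | 1.33 | 9 |
| 400 | 950 | 1,000 | 1,100 | 1.67 | 5 |
| 600 | 1,150 | 1,200 | 1,300 | 2.00 | 1 |

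Only the 600 row can double the stated maximum within a quarter. A 400 start would need (1,200 − 400)/50 = 16 steps. With 12 steps every daily-dose row can pass 600. With 11 steps the 50 row reaches 600 and does not pass it.

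**4. The sections side by side.**

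| Section | Maximum for XR? | Clinic assessment before an XR increase? |
|---|---|---|
| 5.6.1.1 | 600 mcg/day, written for IR | Required, written for IR |
| 5.6.2.1, 7.2.3.3 | None stated | Weekly telephone contact |
| 3.1 | 600 mcg/day, if Table 4 covers XR | Not stated |
| 5.6.2.2 | None stated; cites 5.6.1.1 | None stated; cites 5.6.1.1 |

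**The case against.** The strongest reply is that the 600 mcg/day limit does reach XR. The Section 3.1 paragraph opens with both formulations before it points to Table 4. Section 7.2.3, whose heading covers the Treatment Period for both formulations, contains the XR switch and titration as 7.2.3.3. Section 5.6.2.2 calls the XR Treatment Period identical to the IR one. If its citation was meant for Section 5.6.1.2, that section also leads to Table 4. This stands as a possible reading, so the documents do not support the stronger inference that XR titration simply has no maximum. It does not settle the matter. Table 4 is labelled IR, its steps do not fit 50-mcg increments, and Section 5.6.2.2 places the XR Treatment Period after XR titration and allows uptitration without citing Table 4.

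The second reply is that the clinic condition was written for subjects starting the drug, whereas XR subjects are already on ralinepag, so telephone titration may be a deliberate choice. That is fair. The conflict on this condition comes from the citation of Section 5.6.1.1 in Section 5.6.2.2, and the sponsor need only say which was intended.

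The third reply is that 1,200 mcg is an extreme. That is correct: it needs a subject who switches at the top row and takes all 12 steps, and titration is as needed and limited by tolerability.

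**Conclusion.** The protocol is inconsistent on whether a maximum and a clinic-assessment condition apply to XR increases. Under Section 5.6.2.1 alone, a subject switched to XR 600 mcg passes the stated IR maximum at the first step. The worst case in one quarter is 1,200 mcg/day for that row (1,150 to 1,300 with visit windows). The other daily-dose rows could reach 650 to 1,000 with 12 steps.

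These figures assume a 91-day quarter and one 50-mcg step at every weekly contact. They are what the text permits, not expected doses. They are also nominal micrograms. Table 5 does not convert one to one throughout (IR 120 to XR 100, IR 160 to XR 150), so the ratio of 2.0 is not a ratio of exposure.

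Two further inferences are tempting and not supported:
- The summary of Study APD811-011 in Section 1.1.3, with its "additional 60 mcg dose increments every 5 days up to 30 mcg", might suggest that the upper XR doses lack support. That phrase is an evident misprint in background text and governs no dosing here. Table 5 gives its own XR range, and other support for XR doses may lie outside these documents.
- A reader might infer that the safety results could not be interpreted. SAP Section 9.3.5 lists actual dose, formulation and total daily dose and summarises dose by visit. SAP Section 9.1 summarises weeks on each formulation. Any difference in the doses reached would be visible.

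**What to change.** Reconcile Protocol Sections 3.1, 5.6.1.1, 5.6.1.2, 5.6.2.1, 5.6.2.2 and 7.2.3.3. One statement in Section 5.6.2.1 should say whether a maximum daily dose and a clinic-assessment condition apply to XR increases and, if so, which. Section 3.1 should say whether its reference to Table 4 covers XR. The two citations of Section 5.6.1.1 in Section 5.6.2.2 should be corrected; they appear to be meant for 5.6.1.2 (the IR Treatment Period) and 5.6.2.1 (XR titration). Correcting them is not enough on its own, because 5.6.1.2 leads back to Table 4. The sponsor sets the rule.

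The cost is a few sentences in an amendment and a note with the dosing cards. If a maximum is stated, subjects near it lose some upward flexibility. SAP Section 3 says the study is being discontinued and ongoing subjects are to be combined into ROR-PH-303, so XR titration may already be over and the prospective benefit may be limited.

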5.6.2.2 Treatment Period

After the dose switch and Dose Titration Period with the XR formulation, subjects will continue into the Treatment Period, in which subjects will have an assessment every 3 months. With the exception of the difference in ralinepag formulation, this Treatment Period will be identical to that which occurred with the IR formulation (Section 5.6.1.1, Section 7.2.3).

The optimal dose achieved for each period during the Formulation Switch and Dose Titration Period (Section 5.6.1.1) can be maintained; however, incremental dose changes (uptitration or down titration) will also be allowed during the Treatment Period at the discretion of the Investigator (as clinically indicated).

